10.1.5 Visit 5 to Visit 7/M1 to M3

The following assessments should be done as listed in the study flow chart:

- Blood sample collection for clinical laboratory assessments and urinalysis.
- Blood samples collection for ADA at Visit 5 and Visit 7 and for lymphocyte phenotyping at Visit 5.
- Blood sample collection for thyroid function test at Visit 7.

- Blood samples collection for PK on Visit 5 and Visit 6.
- AE/SAE will be monitored (if any).
- Concomitant medication will be checked and reported (if any).

10.1.6 Visit 8/M4

The following assessments should be done as listed in the study flow chart:

- AE/SAE will be monitored (if any).
- Concomitant medication will be checked and reported (if any).
- Physical examination and vital signs.
- Blood samples collection for clinical laboratory assessments, clinical chemistry, and urinalysis.
- Blood sample collection for lymphocyte phenotyping.
- Perform MRI scan without contrast.
- Perform EDSS assessment.
- Perform SDMT and BVMT-R test.
- Recording of PedsQL/ Ped NeuroQoL.
- Blood samples collection for immune markers (optional).

10.1.7 Visit 9 to Visit 11 /M5 to M7

The following assessments should be done as listed in the study flow chart:

- AE/SAE will be monitored (if any).
- Concomitant medication will be checked and reported (if any).
- Blood samples collection for clinical laboratory assessments, serum creatinine, ALT, and urinalysis, including thyroid function test only at Visit 10.

10.1.8 Visit 12/M8

The following assessments should be done as listed in the study flow chart:

- AE/SAE will be monitored (if any).
- Concomitant medication will be checked and reported (if any).
- Physical examination and vital signs.
- Blood samples collection for clinical laboratory assessments (hematology and chemistry) including urinalysis.
- Blood samples collection for lymphocyte phenotyping.

- Perform MRI scan without contrast.
- Perform EDSS assessment.
- Perform SDMT and BVMT-R test.
- Recording of PedsQL/Ped NeuroQoL.

10.1.9 Visit 13 to Visit 15/M9 to M11

The following assessments should be done as listed in the study flow chart:

- AE/SAE will be monitored (if any).
- Concomitant medication will be checked and reported (if any).
- Blood samples collection for clinical laboratory assessments, serum creatinine, ALT, and urinalysis.
- Perform thyroid function test only at Visit 13.
- The day prior to alemtuzumab administration patient should take the premedication as specified in [Section 1.2.1](#) and [Section 8.2](#).

10.1.10 Visit 16/M12 (second course of alemtuzumab)

Visit 16 (M12) can occur within -7 days or +30 days of the scheduled visit.

The following assessments should be done as listed in the study flow chart:

- Physical examination and vital signs.
- Perform Tanner staging.
- Blood and urine samples collection for clinical laboratory assessments including pregnancy test (for females of childbearing potential), thyroid function test, urinalysis and for ADA.
- Blood samples collection for lymphocyte phenotyping.
- Blood samples collection for PK and immune markers (optional).
- Assess and confirm eligibility for alemtuzumab administration.
- Alemtuzumab will be administered as daily IV infusion on 3 consecutive days in a supervised medical setting. Calculation of the dose used will be based on patient weight. Observation for infusion reactions is recommended during and for at least 2 hours (based on local requirements) after alemtuzumab infusion.
- The Investigator or designee will contact the IVRS to obtain a treatment kit number.
- On days of Alemtuzumab infusion, and 1 hour prior to the infusion, H1 antagonist IV should be administered immediately followed by 30mg/kg or 1000mg IV methylprednisolone (whichever is lower). H2 antagonist medications and NSAID/antipyretic should be administered on the 3 consecutive days of alemtuzumab

administration as needed. Study patients should also receive antiviral prophylaxis for herpetic viral infection beginning on Day 1 and continuing for a minimum of 1 month. If diphenhydramine IV is not available, an equivalent H1 antagonist can be used at an equivalent dosing, via IV route. If no H1 antagonist is available in IV formulation, an oral formulation of an equivalent compound can be used at an equivalent dosing, 2 hours prior to infusion.

- Vital signs during infusion days will be monitored.
- AE/SAE will be monitored (if any).
- Concomitant medication will be checked and reported (if any).

The following infusion management procedures must be utilized for each infusion and each treatment course:

- Pre-infusion :

Physicians should obtain a baseline ECG and vital signs (including heart rate and blood pressure measurement), screen for pre-existing hemorrhagic, cardiovascular (including venous thromboembolism) and cerebrovascular risk factors, screen for lung disease, review concomitant medications (eg, antiplatelet agents, anticoagulants), perform laboratory tests (complete blood count with differential, serum transaminases, serum creatinine, test of thyroid function and urinalysis with microscopy), and evaluate infusion-related risks. Physician should also apply the following contraindications when treating patients in this study:

- Hypersensitivity to the active substance, or to any of the excipients
- Human Immunodeficiency Virus (HIV) infection
- Severe active infection
- Uncontrolled hypertension
- History of arterial dissection of the cervicocephalic arteries
- History of stroke
- History of angina pectoris or myocardial infarction
- Known coagulopathy or on concomitant anti-coagulant therapy

It is at investigator's discretion to treat or not treat patient with alemtuzumab after clinical evaluation.

- During infusion: Continuous/frequent monitoring of heart rate, blood pressure assessment (at least hourly) and overall clinical status of the patients including consideration of the volume of fluids administered. The following are recommendations in case of clinical abnormalities/severe adverse event:
- Interrupt infusion
 - Medically evaluate the patient guided by the adverse event profile of alemtuzumab prior to considering restarting therapy
 - Provide appropriate treatment as needed
 - Consider permanently discontinuing the alemtuzumab infusion if the patient shows clinical symptoms suggesting development of a serious adverse event associated

with the infusion (myocardial ischemia, hemorrhagic stroke, cervico-cephalic arterial dissection or pulmonary alveolar hemorrhage).

- Implement appropriate measures for patients at risk of venous thromboembolism: repeated ambulation during infusion and/or compression stockings.
- Post-infusion: Observation and education of patients
- Observation for infusion reactions is recommended for a minimum of 2 hours after alemtuzumab infusion; 2 hours after infusion, patients should be cautious and reporting if any of the infusion reactions develop within 48 hours.
 - Patients with clinical symptoms suggesting development of a serious adverse event temporarily associated with the infusion (myocardial ischemia, hemorrhagic stroke, cervico-cephalic arterial dissection or pulmonary alveolar hemorrhage) should be closely monitored until complete resolution of the symptoms. The observation time should be extended as appropriate.
 - Patients with persistent blood pressure elevation should be referred to an appropriate medical facility for continued monitoring and treatment.
 - The patients should be educated on the potential for delayed onset of infusion associated reactions and symptoms and signs of cardiovascular or cerebrovascular events, and instructed to report symptoms and/or seek appropriate medical care.
- Perform MRI scan without contrast.
 - Perform EDSS assessment.
 - Perform SDMT and BVMT-R test.
 - Recording of PedsQL/Ped NeuroQoL.

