1.2.2 Schedule of events Part 2 (Year 2)

Table 2 - Schedule of events in Year 2

Visit Day ^a	M13	M14	M15	M16	M17	M18	M19	M20	M21	M22	M23	M24 (EOTP)	Relapse Visit ^b
Visit number	V17	V18	V19	V20	V21	V22	V23	V24	V25	V26	V27	V28	
Treatment:													
Efficacy:													
EDSS			X			X			X			X	X
Brain MRI ^c												X	
SDMT						X						X	
BVMT-R Test						X						X	
PedsQL (QoL Questionnaire)/ Ped. NeuroQoL (subcomp.) ^d						X						X	
Safety:													
Physical examination ^e			X			X			X			X	X
Clinical chemistry laboratories ^f			X			X			X			X	
Hematology (Differential CBC) ^f	X	X	X	X	X	X	X	X	X	X	X	X	
Thyroid Function Tests ^g			X			X			X			X	
Urinalysis ^h	X	X	X	X	X	X	X	X	X	X	X	X	
Serum Creatinine and alanine aminotransferase	X	X		X	X		X	X		X	X		
Lymphocyte phenotyping	X		X			X			X			X	
Samples for antibodies to Study Drug	X		X									X	
Tanner Staging ⁱ												X	
Concomitant medications	←												→
AE/SAE recording (if any)	←												→
Vital Signs			X			X			X			X	X
HPV ^j (yearly)	←												→
Laboratory testing:													
PK sampling ^k	X ^k	X ^k											
Immune Marker Sampling (optional)						X						X	

Abbreviations: AE: adverse event; BVMT-R: brief visuospatial memory test-revised; CBC: complete blood count; EDSS: Expanded Disability Status Scale; EOTP: end of treatment phase; M: month(s); MRI: magnetic resonance imaging; Neuro-QoL: quality of life in neurological disorders; Ped: pediatric; PK: pharmacokinetics; QoL: quality of life; SAE: serious adverse event; SDMT: symbol digit modality test.

- a* Recommended windows: The window for obtaining samples and performing assessments at any given visit will be ± 7 days, except for the D-14 to D-7 visit which should occur between -7 to -1 days prior to M0/D1. All post M0/D1 treatment period assessments should be completed within ± 7 days of the scheduled visit date relative to the M0/D1 visit.
- b* This visit is only required for subjects that have a suspected relapse, and should occur within 7 days following the occurrence of the clinical event.
- c* The MRI assessments will be available to investigators to assess safety.
- d* PedsQL questionnaire (Paediatric Quality of Life Inventory) will be completed by patients/parents based on questionnaire recommendations. Peds NeuroQoL is a quality of life measurement developed for neurological disorders and consists of short form questions for multiple domains. Specific sub-domains will be utilized.

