- i* Tanner stage to be assessed as noted until complete sexual maturity.
- j* Testing will be conducted for human papillomavirus (HPV) infection as and when recommended by local public health authorities. If the testing is positive, the patient may be eligible after the condition has resolved as per the Investigator opinion (eg, follow-up HPV test is negative or cervical abnormality has been effectively treated). An annual follow-up is recommended.
- k* For details on PK sampling, refer to [Section 1.2.5](#).

1.2.3 Schedule of events Part 3 (Safety monitoring phase Year 3 - Year 5)

Table 3 - Safety monitoring phase Year 3-5

	Safety monitoring phase												
Visit Day ^a	M25	M26	M27	M28	M29	M30	M31	M32	M33	M34	M35	M36 ^b	Relapse Visit
	M37	M38	M39	M40	M41	M42	M43	M44	M45	M46	M47	M48 ^b	
	M49	M50	M51	M52	M53	M54	M55	M56	M57	M58	M59	M60 ^b	
Visit number	V29	V30	V31	V32	V33	V34	V35	V36	V37	V38	V39	V40	
	V41	V42	V43	V44	V45	V46	V47	V48	V49	V50	V51	V52	
	V53	V54	V55	V56	V57	V58	V59	V60	V61	V62	V63	V64	
Efficacy:													
EDSS						X						X	X
Brain MRI ^c												X	
SDMT												X	
BVMT-R Test												X	
PedsQL (QoL Questionnaire)/ Ped. NeuroQoL (sub-comp.)												X	
Safety:													
Physical examination						X						X	X
Clinical chemistry laboratories ^{d,e}			X			X			X			X	
Hematology (Differential CBC) ^{d,f}	X	X	X	X	X	X	X	X	X	X	X	X	
Thyroid Function Tests ^d			X			X			X			X	
Urinalysis ^g	X	X	X	X	X	X	X	X	X	X	X	X	
Serum Creatinine ^h and alanine aminotransferase ^d	X	X		X	X		X	X		X	X		
Lymphocyte phenotyping												X	
Samples for antibodies to Study Drug												X	
Tanner Staging												X	
AE/SAE recording (if any)	←-----→												
Concomitant medications	←-----→												
Vital Signs						X						X	X
HPV ⁱ (yearly)	←-----→												

Abbreviations: AE: adverse event; BVMT-R: brief visuospatial memory test-revised, CBC: complete blood count; EDSS: Expanded Disability Status Scale; M: month(s);

MRI: magnetic resonance imaging; Neuro-QoL: quality of life in neurological disorders; Ped: paediatric; QoL: quality of life; SAE: serious adverse event; SDMT: symbol digit modality test.

a All study visits during safety monitoring phase except the M36,M48 and M60 visits can be performed within ±7 days.

b M36, M48 and M60 Study visits can be performed within ±4 weeks for these visits, to allow for scheduling of assessments.

- c* The MRI assessments will be available to investigators to assess safety.

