Most patients treated with alemtuzumab in controlled clinical trials in MS experienced mild to moderate IARs during or soon after alemtuzumab 12 mg administration. Common IARs include headache, rash, pyrexia, nausea, urticaria, pruritus, insomnia, chills, flushing, fatigue, dyspnea, dysgeusia, chest discomfort, generalized rash, tachycardia, dyspepsia, dizziness, and pain. Serious reactions occurred in 3% of patients including cases of pyrexia, urticaria, atrial fibrillation, nausea, chest discomfort, and hypotension. In addition, anaphylaxis has been reported rarely. Prophylactic use of corticosteroids was useful in alleviating IARs and is part of the recommended prescribing information for alemtuzumab use in MS patients. In addition, modification of the duration of infusion is permitted to help patients tolerate infusions if needed and symptomatic medications such as antihistamines and/or antipyretics were administered often in the studies.

Alemtuzumab treatment increases the risk of autoimmune-mediated conditions. Autoimmune thyroid disorders occurred in 36 % of patients in clinical trials in MS through 4 years following first exposure. Observed autoimmune thyroid disorders included hyperthyroidism and hypothyroidism, which occurred at similar rates. Serious thyroid related events occurred in <1% patients. No consistent pattern was observed with regards to time of onset after treatment initiation, although the highest incidence of thyroid adverse events (AEs) was observed in Year 3 after the first treatment course. Therefore, as part of the risk minimization strategy for autoimmune disorders, thyroid function tests must be obtained prior to the initiation of alemtuzumab treatment and every 3 months thereafter until 48 months following the last infusion. This will allow the timely detection and treatment of thyroid disorders for patients treated with alemtuzumab.

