Immune thrombocytopenia and nephropathies, including antiGBM disease, although potentially more serious than thyroid disorders, were observed infrequently. Serious events of ITP have been observed in approximately 1% of patients treated with alemtuzumab in clinical trials in MS. Fatality in the index case of ITP, which was reported in the Phase 2 study, highlights the seriousness of the risks associated with the disorder. However, risk minimization measures including patient education and monthly complete blood counts (CBCs) introduced to monitor for ITP and other potential autoimmune cytopenias in the clinical studies allowed the prompt diagnosis and treatment of patients who subsequently developed these conditions. AntiGBM disease was reported rarely in the clinical program. Nephropathies including antiGBM disease have been observed in controlled clinical trials in MS. Patient education and monthly testing of serum creatinine were effective in identifying cases early to allow prompt treatment. Similarly, urinalysis testing was also effective in identifying nephropathies during the clinical studies. Accordingly, monthly testing including CBC with differential, platelet count and monitoring for any cytopenia as well as serum creatinine testing and urinalysis with microscopy, must be obtained prior to treatment with alemtuzumab and every month thereafter until 48 months following the last infusion. This will facilitate the early detection and treatment of these disorders, should they occur.

Infections occurred in 71% of patients treated with Lemtrada® 12 mg as compared to 53% of patients treated with Rebif® (IFNB-1a) in controlled clinical trials in MS up to 2 years in duration and were predominantly mild to moderate in severity. Serious infections occurred in 2.7% of patients treated with alemtuzumab as compared to 1.0% of patients treated with IFNB-1a in controlled clinical trials in MS. The most frequent infections reported in alemtuzumab-treated

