6 STUDY DESIGN

6.1 DESCRIPTION OF THE STUDY

This is an open-label, rater-blinded, single-arm, before and after switch study of efficacy, safety and tolerability of alemtuzumab in paediatric patients from 10 to <18 years of age with RRMS with disease activity on prior DMT.

The study will consist of:

- **Screening period** (0-28 days prior to M-4) - Patients and parents will receive information on the study and on alemtuzumab. Inclusion/exclusion criteria will be reviewed. After informed consent signature, screening assessments for eligibility will be performed. Screening assessments may require more than one visit within the screening period which may last a maximum of 28 days.
- **Prior DMT phase (approximately 4 months): M-4 to M0**
 - **Eligibility confirmation visit:** At the end of the screening period (at M-4) patients/parents will come to the site to confirm patient is eligible for the study. Investigator will check that all assessment allow patient inclusion. During this visit patients will be reminded to continue their prior DMT (limited to interferon or GA only).
 - **From M-4 visit to D-14 to D-7:** Phone calls (approximately every month) will be done, to remind patients to continue on their DMT and check patient status.
 - **Day -14 to D-7 visit:** Investigator will confirm patient is eligible for alemtuzumab administration and will tell the patient to discontinue current DMT 7 days prior to administration of first dose of alemtuzumab at Month 0.
- **Alemtuzumab treatment phase** (approximately 2 years) – This phase starts with administration of first dose of alemtuzumab at M0, after discontinuation of current DMT, and ends at M24. The second dose of alemtuzumab will be administered at M12. The MRI based primary efficacy endpoint will be assessed over a 4 month period during this phase compared to an equal period during the prior DMT phase.

Note: end of treatment phase (EOTP) refers to the end of the alemtuzumab treatment phase (see graphic study design [[Section 1.1](#)]).
- **Safety monitoring phase** (approximately 3 years) – Additional safety follow-up and monitoring for all patients treated with alemtuzumab will be conducted during this phase to yield a total of 5 years of follow-up since first alemtuzumab treatment, including 4 years post last treatment with alemtuzumab.

Note: end of study (EOS) refers to the end of the safety monitoring phase (see graphic study design [[Section 1.1](#)]).

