6.2 DURATION OF STUDY PARTICIPATION

6.2.1 Duration of study participation for each patient

The maximum study duration per patient will be approximately 5 years and 5 months:

- **Screening period:** 0-28 days prior to M-4 from signed informed consent to eligibility confirmation.
- **Prior DMT phase:** approximately 4 months from signed informed consent and screening qualification to prior DMT discontinuation. **Alemtuzumab treatment phase:** approximately 2 years, from first dose alemtuzumab administration to one year after last dose of alemtuzumab administration.
- **Safety monitoring phase:** approximately 3 years to complete the 48 months safety follow-up post last treatment with alemtuzumab.

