6.2.2 Determination of end of clinical trial (all patients)

The EOS is defined as being the “last patient last visit” planned with the protocol. The last patient visit will be considered when the last patient has completed safety monitoring phase (M60). The Sponsor reserves the right to discontinue the study at any time.

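### A second course given late in its +30-day window leaves M0-dated visits and the M60 end of study in conflict with monitoring to 48 months after the last infusion

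*Protocol*

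**What the plan says.** Course 2 is three consecutive daily infusions, nominally 12 months after course 1. Section 10.1.10 gives it an asymmetric window: "Visit 16 (M12) can occur within -7 days or +30 days of the scheduled visit".

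Two anchors then govern what follows.

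- **First dose.** Table 2, footnote a (Section 1.2.2) places treatment-period assessments within 7 days "of the scheduled visit date relative to the M0/D1 visit". Section 6.2.2 ties the end of the trial to M60, and Section 11.4.3.1 closes the on-treatment adverse event period at Month 60.
- **Last dose.** Section 4 says that blood counts, creatinine and urinalysis must be done "every month thereafter until 48 months following the last infusion", and thyroid tests "every 3 months thereafter until 48 months following the last infusion". Section 6.2.1 says that the safety monitoring phase exists "to complete the 48 months safety follow-up post last treatment with alemtuzumab", and ends the treatment phase one year after the last dose.

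Section 6.1 puts both into one sentence: follow-up is "to yield a total of 5 years of follow-up since first alemtuzumab treatment, including 4 years post last treatment with alemtuzumab". Table 3, footnote b (Section 1.2.3) adds that "M36, M48 and M60 Study visits can be performed within" 4 weeks either side.

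Visit 17 (M13) carries PK, lymphocyte phenotyping and anti-drug antibody samples (Table 2, Section 10.1.11). Table 5 (Section 1.2.5) lists the course 2 PK samples in order: Day 1 predose (S1), Day 3 end of infusion (S2), Day 12 (S3), M13 (S4) and M14 (S5). Section 11.4.4 summarises pharmacodynamic (PD) endpoints by scheduled visit.

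**The concern.** Five years from the first dose contains four years from the last dose only if the second course starts no later than Month 12. The protocol permits a start up to 30 days after that, and nothing visible says which anchor prevails.

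Two things follow for a late patient. First, a site can keep exactly to the visit schedule and still stop monitoring before the 48-month minimum that Section 4 makes mandatory. That minimum is there to detect delayed autoimmunity, here in children. Second, on M0 dates the post-course-2 samples slide toward the infusion. M13 is the most exposed: a sample meant to describe the patient a month after dosing could be taken during the infusions or even before them. A summary by scheduled visit would then pool it with true one-month samples. M14 and M15 remain post-dose samples, but earlier than intended.

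**Working it through.** **Inputs.** Course 2 window −7 to +30 days (Section 10.1.10); three infusion days, so the last infusion is Day 1 + 2 days; M60 window ±28 days (Table 3, footnote b); required monitoring 48 months after the last infusion (Section 4); M13 PK window ±2 days (Table 5, footnote a); other Year 2 windows ±7 days (Table 2, footnote a). One month is taken as 30.4375 days.

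**The plan's own figure.** 60 − 12 = 48 months, which matches Section 6.1 when course 2 is on time, apart from the 2 days of infusion.

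**Monitoring shortfall.** Let *d* be the delay of course 2 in days and *w* the number of days by which M60 is late.

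- Last infusion = 365.25 + *d* + 2 days after M0.
- 48 months later = 365.25 + *d* + 2 + 1461.
- M60 visit = 1826.25 + *w*.
- Days short = *d* + 2 − *w*.

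| Delay *d* | M60 on time (*w* = 0) | M60 at end of window (*w* = 28) |
|---|---|---|
| 0 | 2 | none (26 to spare) |
| 14 | 16 | none (12 to spare) |
| 26 | 28 | 0 |
| 30 | 32 | 4 |

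At *d* = 30 the patient has 1826.25 − 397.25 = 1429 days after the last infusion, or 46.95 months, with M60 on time. With M60 at +28 days it is 1457 days, or 47.87 months. The window also runs the other way: M60 at −28 days with *d* = 30 is 30 + 2 + 28 = 60 days short. Calendar dates for four different start dates give the same day counts.

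**Course 2 sample timing on M0 dates.** Days from course 2 Day 1 to visit M*k* = (*k* − 12) × 30.4375 − *d*.

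| Delay *d* | M13 | M14 | M15 |
|---|---|---|---|
| 0 | 30.4 | 60.9 | 91.3 |
| 20 | 10.4 | 40.9 | 71.3 |
| 30 | 0.4 | 30.9 | 61.3 |

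- At *d* = 30, the M13 PK sample with its ±2-day window falls between −1.6 and +2.4 days from Day 1.
- The Day 12 sample (S3) is 11 days after Day 1. M13 (S4) precedes it when 30.4375 − *d* < 11, that is, from a delay of 20 days. This reverses the Table 5 order.
- With the ±7-day window, an M13 lymphocyte or antibody sample can precede dosing when 30.4375 − *d* − 7 < 0, that is, from a delay of 24 days.

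**The case against.** The best counter-argument is that Section 6.2.1 already supplies the rule. It defines both phases by the last dose, so M60 can be read as a nominal label, and phase lengths are described as approximate. Table 2 calls its windows recommended, and its footnote looks generic, since it still mentions the pre-dose visit. Table 5 is plainly a course 2 schedule, and a site that followed M0 dates into an M13 visit before or during the infusions would see the absurdity. The safety-phase footnotes name no anchor. The Year 1 window footnote, which may say more about the second course, is not in the available text. How PD samples are windowed for analysis normally belongs in the statistical analysis plan. The gap is small: 32 of 1,461 days is 2.2%, and 4 days is 0.3%. Ongoing serious events and events of special interest are followed past study end (Section 10.4.3).

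Much of this limits the size of the problem and is accepted. A sensible site may well date M13 and M14 from the actual infusion, and the analysis windows can be left to the analysis plan. It does not remove the contradiction. The only explicit anchor in Table 2 is M0/D1, and Section 6.1 counts five years from first treatment. No visible text tells a site to re-date visits or hold M60 late. Following events already known at study end does not replace the tests meant to detect new ones.

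**Conclusion.** The concern holds, as a minor point to correct. For any delay of course 2, an on-time M60 leaves the patient *d* + 2 days short of the protocol's own minimum, up to 32 days. Delays up to 26 days can be absorbed, but only by scheduling M60 late, which nothing visible requires. Delays of 27 to 30 days cannot be fully absorbed even then. On M0 dating, the M13 PK, lymphocyte and antibody samples lose their intended meaning as the delay approaches 30 days.

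This rests on reading Table 2's M0/D1 anchor as written and on taking M60 from the first dose, as the five-year wording in Section 6.1 implies. The documents do not say how many patients were dosed late. The primary endpoint is unaffected because it ends at M8, and AUClast is calculated to the real time of the last sample (Table 8).

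**What to change.** - State in Section 10.1.10 and Table 2, footnote a, that visits after M12 are dated from the actual course 2 Day 1, with safety tests kept monthly across the transition.
- State in Table 3 and Section 6.2.2 that each patient's monitoring ends at the later of M60 and 48 months after the last infusion, in line with Section 6.2.1. Align the Month 60 limit of the on-treatment adverse event period in Section 11.4.3.1, so that events in the added days are counted.
- For samples already taken on M0 dates, summarise course 2 PK, PD and antibody results by actual days since course 2 Day 1. This can be placed in the statistical analysis plan and needs no new data.

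The cost is amendment wording, with the approvals that Section 15 requires, and at most about 32 extra days of follow-up for a patient dosed 30 days late. No new procedures are needed beyond the monthly tests due in that time.
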